### **3.7. End of Study**

End of Study is defined as when the last subject has completed 58 weeks of treatment plus 30 days follow-up.

### **3.8. Post Study Care**

All subjects completing all study related procedures, including endoscopy at Week 58, will be offered an opportunity to participate in the LTE study (GS-US-419-3896). For those subjects who do not participate in the LTE study, after the subject has completed their study participation, the long-term care of the participant will remain the responsibility of their primary treating physicians.

CCI [REDACTED]

[REDACTED] [REDACTED]

[REDACTED]

- | [REDACTED]
- | [REDACTED]
- | [REDACTED]
- | [REDACTED]
- | [REDACTED]
- | [REDACTED]
- | [REDACTED]
- | [REDACTED]

[REDACTED]

[REDACTED]

[REDACTED]

[REDACTED]

CCI

[Redacted]

[Redacted]

[Redacted]

[Redacted]

CCI

[Redacted]

[Redacted]

[Redacted]

## **4. SUBJECT POPULATION**

### **4.1. Number of Subjects and Subject Selection**

#### **Cohort A Induction Study**

Approximately 660 subjects who meet the eligibility criteria at screening will be randomized in a blinded fashion in a 1:1:1 ratio to filgotinib 200 mg, filgotinib 100 mg, or matching placebo.

#### **Cohort B Induction Study**

Approximately 660 subjects who meet the eligibility criteria at screening will be randomized in a blinded fashion in a 1:1:1 ratio to filgotinib 200 mg, filgotinib 100 mg, or matching placebo.

#### **Maintenance Study**

Subjects from Cohorts A and B who achieve either clinical remission by PRO2 or endoscopic response at Week 10 will be re-randomized at Week 11 in a blinded fashion in a 2:1 ratio to either the same dose of filgotinib or placebo. Refer to Section 3.3, [Table 3-1](#).

In order to manage the total study enrollment, the Sponsor, at its sole discretion, may suspend screening and/or enrollment at any site or study-wide at any time.

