### **Stratification Factors (Maintenance Study)**

- History of exposure to a biologic agent (Yes or No)
- Concomitant use of oral, systemically absorbed corticosteroids (eg, prednisone) at Day 1, (Yes or No)
- Concomitant use of immunomodulators (eg, 6-mercaptopurine [6-MP], azathioprine, methotrexate [MTX]) at Day 1, (Yes or No)

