## 8.9. Sample Size

### 8.9.1. Induction Studies (Cohorts A and B)

The sample size was chosen to ensure that a clinically meaningful difference in both clinical remission rate by CDAI at Week 10 and endoscopic response rate at Week 10 could be detected when comparing filgotinib 200 mg to placebo within each Induction Study.

A sample size of 220 subjects in each treatment group (n = 660 total) will provide an overall power of 97% for a filgotinib 200 mg group comparison to placebo at a 2-sided 0.05 significance level to detect a treatment difference of 20% in clinical remission rate by CDAI at Week 10 (45% on filgotinib 200 mg and 25% on placebo) and a treatment difference of 15% in endoscopic response rate at Week 10 (25% on filgotinib 200 mg and 10% on placebo). Since each end point needs to achieve statistical significance, the overall power of 97% is calculated as the product of the two individual powers based on each end point.

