### 8.9.2. Maintenance Study

Assuming an Induction response rate (ie, proportion of subjects achieving clinical remission by PRO2 or endoscopic response at Week 10) of 40% among subjects receiving filgotinib 200 mg or filgotinib 100 mg treatment, approximately 176 subjects from each filgotinib dose group from Cohorts A and B Induction Studies combined would be eligible to be re-randomized into the Maintenance Study.

The sample size was chosen to ensure that a clinically meaningful difference in both clinical remission rate by CDAI and endoscopic response rate at Week 58 could be detected when comparing filgotinib 200 mg to placebo in the Maintenance Study.

A sample size of 60 subjects in the placebo group and 120 subjects in the filgotinib group at the same dose level as the induction dose will provide an overall 94% power for a filgotinib 200 mg comparison to placebo at a 2-sided 0.05 significance level to detect a treatment difference of 30% in maintenance clinical remission rate by CDAI at Week 58 and maintenance endoscopic response rate at Week 58 (50% on filgotinib 200 mg and 20% on placebo). Since each end point needs to achieve statistical significance, the overall power of 94% is calculated as the product of the two individual powers based on each end point.

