**Note:** The worst outcome of a prior treatment is treatment failure, followed by intolerance, and then other outcomes.

— Prior failure of both TNF- $\alpha$  antagonist and vedolizumab

- Yes (dual refractory, defined as those who have failed at least 2 classes of biologic therapies [any TNF- $\alpha$  antagonist and vedolizumab])
  - United States (US)/Korea Males
  - Subjects other than US/Korea Males

- No
  - US/Korea Males
  - Subjects other than US/Korea Males
- Concomitant treatment at baseline (or maintenance baseline for Maintenance Study)
  - Concomitant use of systemically absorbed corticosteroid and/or immunomodulator at baseline/maintenance baseline, including: a) systemically absorbed corticosteroid only, b) immunomodulator only, c) both, and d) neither;
  - Prednisone equivalent dose for subjects who are on systemically absorbed corticosteroid at baseline/maintenance baseline (mg/day)
  - Prednisone equivalent dose for subjects who are on systemically absorbed corticosteroid at baseline/maintenance baseline (> 0 to 10 mg/day, > 10 to 20 mg/day, > 20 - 30 mg/day, >30 mg/day)
  - Concomitant use of 5-aminosalicylates (yes, no) at baseline/maintenance baseline

In addition, another baseline characteristics table for Maintenance Study using the FAS will be generated, including the above baseline characteristics except those marked as “Induction Studies only” and the following additional variables:

- CDAI score at maintenance baseline
- PRO2 subscores at maintenance baseline: abdominal pain and liquid or very soft stool subscores
- Total PRO2 score at Week 10
- Total SES-CD score at Week 10
- Clinical remission by CDAI (yes, no) at Week 10
- Clinical response by CDAI (yes, no) at Week 10
- Clinical remission by PRO2 (yes, no) at Week 10
- Endoscopic response (yes, no) at Week 10
- CCI [REDACTED]
- CCI [REDACTED]

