**Table 6-1. Definitions of Selected Efficacy Endpoints**

Study	Type	Endpoint	Definition
Induction	EU: secondary Non-EU: Co-primary	Clinical remission by CDAI at Week 10	CDAI score < 150 points at Week 10
Induction	Co-primary	Endoscopic response at Week 10	≥ 50% reduction from baseline in total SES-CD score at Week 10 based on central reading
Induction	EU: co-primary Other: Secondary	Clinical remission by PRO2 at Week 10	Abdominal pain score ≤ 1 (on a scale of 0 to 3) and liquid or very soft stool (Bristol stool scale type 6 or 7) frequency ≤ 3 at Week 10
Induction	Secondary	Clinical response by CDAI at Week 10	Reduction in CDAI score from Induction baseline by at least 100 points or CDAI score < 150 at Week 10
Induction	CCI	CCI	CCI
Induction	EU: Secondary Non-EU: CCI	Both clinical remission by PRO2 and endoscopic response at Week 10	Clinical remission by PRO2 and endoscopic response at Week 10 combined into a single endpoint on a patient level
Induction	CCI	CCI	CCI
Induction	CCI	CCI	CCI
Induction	CCI	CCI	CCI
Maintenance	Co-primary	Clinical remission by CDAI at Week 58	CDAI score < 150 points at Week 58

Study	Type	Endpoint	Definition
Maintenance	Co-primary	Endoscopic response at Week 58	≥ 50% reduction from Induction baseline in total SES-CD score at Week 58 based on central reading
Maintenance	Secondary	Clinical remission by PRO2 at Week 58	Abdominal pain score ≤ 1 (on a scale of 0 to 3) and liquid or very soft stool (Bristol stool scale type 6 or 7) frequency ≤ 3 at Week 58
Maintenance	Secondary	Clinical response by CDAI at Week 58	Reduction in CDAI score from Induction baseline by at least 100 points or CDAI score < 150 at Week 58
Maintenance	Non-EU: secondary	Sustained clinical remission by CDAI at Weeks 10 and 58	Clinical remission by CDAI at both Week 10 and Week 58
Maintenance	Non-EU: secondary	6-month Corticosteroid-free clinical remission by CDAI at Week 58	Clinical remission by CDAI with no corticosteroid use for the indication of CD for at least 6 months prior to Week 58 among subjects who are on corticosteroid at maintenance baseline (baseline of Maintenance Study). Subjects who weaned off steroids but required re-initiation within 6 months prior to Week 58 assessment will be considered to have not met this endpoint.
Maintenance	Secondary	Sustained clinical remission by PRO2 at Weeks 10 and 58	Clinical remission by PRO2 at both Week 10 and Week 58

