##### Cohort B Induction Study:

- Number of prior exposures to biologic agent ( $\leq 1$ , > 1) as listed in [Appendix 2](#)
- Concomitant use of oral, systemically absorbed corticosteroids at Day 1
- Concomitant use of immunomodulators at Day 1

For the Maintenance Study, a stratified CMH test will be used to compare the treatment effect between a filgotinib dose group and placebo among the subjects from Induction Cohorts A and B combined being treated with the same dose of filgotinib. The CMH test will be stratified by the following factors:

- History of exposure to a biologic agent, (Yes or No)
- Concomitant use of oral, systemically absorbed corticosteroids at maintenance baseline
- Concomitant use of immunomodulators at maintenance baseline

Stratification factors based on the clinical database will be used for the analysis. The stratified CMH chi-square p-value for each of the above comparison will be provided. Strata with low numbers of subjects might be aggregated for the analysis. The 2-sided 95% CI of clinical remission rate by CDAI and endoscopic response rate based on normal approximation method with a continuity correction will be provided for each treatment group. In addition, stratified proportion difference along with its 95% 2-sided CI using stratum-adjusted Mantel-Haenszel (MH) approach {Koch 1989} for each comparison will be provided as follows:

The stratified point estimates for difference in proportion of subjects achieving an endpoint between each filgotinib (F) treatment group and the placebo (P) group will be calculated following formula (1).

$$\hat{p}_F - \hat{p}_P = \frac{\sum W_h d_h}{\sum W_h} \quad (1)$$

where  $d_h = \hat{p}_{Fh} - \hat{p}_{Ph}$  is the difference in the proportion of subjects who achieved the endpoint between the filgotinib group and the placebo group in stratum  $h$  ( $h = 1, 2, \dots, K$ ), and  $W_h = \frac{n_{Fh}n_{Ph}}{n_{Fh}+n_{Ph}}$  is the weight based on the harmonic mean of sample size per treatment group for each stratum where  $n_{Fh}$  and  $n_{Ph}$  are the sample sizes of the filgotinib group and the placebo group in stratum  $h$ , respectively.

The 95% stratum-adjusted MH CIs will be calculated following formula (2).

$$\hat{p}_F - \hat{p}_P \pm Z_{1-\alpha/2} \cdot SE(\hat{p}_F - \hat{p}_P) \quad (2)$$

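### The Maintenance test of Week 58 endoscopic response is valid but does not adjust for Week 10 endoscopic response, the same endpoint measured earlier; adding it would give a modest gain in precision

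*Protocol*

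**What the plan says.** **Entry.** Protocol 4.1 (Maintenance Study) says that subjects "who achieve either clinical remission by PRO2 or endoscopic response at Week 10 will be re-randomized at Week 11". Either criterion is enough. Allocation is 2:1, the induction dose against placebo.

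**Endpoint.** SAP Table 6-1 defines endoscopic response at Week 58 as a "reduction from Induction baseline in total SES-CD score at Week 58 based on central reading" of at least 50%. The reference is Induction baseline, not Week 10.

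**Factors.** The Maintenance re-randomisation factors in Protocol 3.3 are "History of exposure to a biologic agent (Yes or No"), Day 1 corticosteroid use and Day 1 immunomodulator use. SAP 1.2.2 adds that Cohort A or B took the place of biologic history until Cohort B enrolment closed. The Maintenance CMH factors in SAP 6.2.4 are biologic history, corticosteroid use at maintenance baseline, and "Concomitant use of immunomodulators at maintenance baseline". Week 10 response is in none of these lists, and none of the lists is redacted. SAP 6.2.4 also allows strata with few subjects to be aggregated, but gives no rule.

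**Where Week 10 endoscopic status is used.** SAP 5.2 tabulates "Endoscopic response (yes, no) at Week 10" for the Maintenance Full Analysis Set. SAP 6.2.5.4 cross-tabulates Week 58 outcome by Week 10 outcome. SAP 6.2.5.3 puts maintenance-baseline segment scores into the imputation model of a sensitivity analysis. None of these adjusts the primary comparison.

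**The concern.** Week 10 endoscopic response is the co-primary endpoint itself, read 48 weeks earlier by the same central process. It is known before re-randomisation, because it helps to decide eligibility, and the trial already derives it. A factor of this kind would normally be the first candidate for adjustment, yet the test neither balances nor adjusts for it.

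Two things are at stake. If the factor is prognostic, the unadjusted comparison carries variance that could be removed. And with about 59 placebo subjects per dose, the arms can differ by chance in the share who start with the response; a visible imbalance would invite argument about post hoc adjustment. The endpoint matters: each dose must win it together with clinical remission, and under Protocol 8.5.3.2 a 200 mg failure on either co-primary ends formal testing.

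**Working it through.** **1. The plan's own power (Protocol 8.9.2).** Inputs: 60 placebo, 120 filgotinib, 20% v 50%, two-sided 0.05, joint power as the product of two equal powers. With a continuity correction:
- corrected difference = 0.30 − 0.5 × (1/60 + 1/120) = 0.2875
- null SE = √(0.4 × 0.6 × (1/60 + 1/120)) = 0.0775
- alternative SE = √(0.2 × 0.8/60 + 0.5 × 0.5/120) = √0.00475 = 0.0689
- power = Φ((0.2875 − 1.96 × 0.0775)/0.0689) = 97.6%; squared, 95.2%

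The plan states 94%, so the figure is reproduced closely. (Uncorrected: 98.4% and 96.9%. Fisher exact: 97.8% and 95.7%.) At the planned effect there is little power left to gain.

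**2. Share entering without endoscopic response, 200 mg.** Protocol 8.9.2 starts from "Assuming an Induction response rate (ie, proportion of subjects achieving clinical remission by PRO2 or endoscopic response at Week 10) of 40" per cent, and 8.9.1 from a "treatment difference of 15% in endoscopic response rate at Week 10 (25% on filgotinib 200 mg and 10% on placebo"). Section 8.9.1.1 gives 30% for PRO2 remission.
- both criteria: 30 + 25 − 40 = 15%
- PRO2 only: 30 − 15 = 15%; endoscopic only: 25 − 15 = 10%
- share without endoscopic response: 15/40 = 37.5%, or 66 of the 176 expected

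**3. Chance imbalance.** Splitting 176 in a 2:1 ratio gives about 117 v 59. SD of the between-arm difference = √(0.625 × 0.375 × (1/117 + 1/59)) = 0.077. The chance that it exceeds 10 points is about 20%.

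**4. Variance removed.** The documents do not say how far Week 10 response predicts Week 58 response, so this is an assumption. Let RR be the ratio of Week 58 response rates, Week 10 responders to non-responders, equal in both arms, with overall rates held at 50% v 20%. For RR = 3 the stratum rates are 66.7%/22.2% on filgotinib and 26.7%/8.9% on placebo:
- filgotinib: (0.625 × 0.667 × 0.333 + 0.375 × 0.222 × 0.778)/120 = 0.00170
- placebo: (0.625 × 0.267 × 0.733 + 0.375 × 0.089 × 0.911)/60 = 0.00254
- sum 0.00424 against 0.00475 unadjusted: 11% less variance

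The same calculation gives 0% for RR 1, 5% for RR 2 and 18% for RR 5.

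**5. Simulated CMH power (%).** 120 v 60 subjects, 20,000 trials per row. Assumed splits: 70/30 for biologic history, 35/65 for each of the other two factors; none of the three is prognostic. 'Pooled' adds Week 10 response and collapses fully over immunomodulator use (8 strata). 'Crossed' adds it with no pooling (16 strata).

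| RR | 50 v 20: planned | pooled | crossed | 40 v 20: planned | pooled | crossed |
|---|---|---|---|---|---|---|
| 1 | 97.9 | 97.8 | 97.3 | 77.2 | 77.3 | 75.4 |
| 2 | 97.9 | 98.5 | 98.3 | 77.5 | 79.4 | 77.7 |
| 3 | 98.0 | 98.8 | 98.6 | 76.8 | 81.3 | 79.5 |
| 5 | 97.7 | 99.3 | 99.1 | 77.2 | 83.6 | 82.5 |

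At 20% v 20%, two-sided rejection stays between 4.8% and 5.1% for all three tests. The 40% v 20% case is an assumption, not a plan figure. At those rates RR 2 corresponds to odds ratios of about 2.3 (placebo) and 3.0 (filgotinib), and RR 3 to about 3.7 and 5.3.

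Separate runs set up in odds ratios, with Week 10 response replacing immunomodulator use (the same 8 strata as 'pooled'), gave gains of about 0.3 to 1.2 points at 50% v 20% and 1.5 to 5.5 at 40% v 20% for odds ratios of 2 to 6. Another run at 117 v 59 found 0.4 and 0.8 points at an odds ratio of 2, and 5.2 points (76.5 to 81.7) at 40% v 20% with an odds ratio of 6. When immunomodulator use was given the same odds ratio of 2 as Week 10 response, full collapse gained nothing (98.0 v 98.0; 77.1 v 77.0).

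**The case against.** The strongest reply is that nothing is wrong. Choosing which prognostic factors to adjust for is a design judgement, the documents are consistent, and endoscopic power at the planned effect is already about 97.5%. The prognostic strength is the reviewer's assumption. A fully crossed fourth factor makes 16 strata for about 176 subjects, 11 on average, and loses up to about 2 points if Week 10 response is uninformative. Dropping a randomisation factor to make room would conflict with Protocol 8.5.1, which adjusts each primary endpoint for the stratification factors. All of this stands. It limits the size of the point and rules out simply swapping one factor for another.

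An analyse-as-randomised argument against adding a factor is weaker. The SAP already analyses steroid and immunomodulator use at maintenance baseline although re-randomisation used Day 1 values, and uses biologic history where early subjects were stratified by cohort.

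The baseline table and cross-tabulation will show an imbalance but not correct for it. Some subgroup bullets in SAP 6.2.7 are redacted, so a Week 10 subgroup analysis cannot be excluded; that would not adjust the primary test either.

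A reader might infer three stronger things that the documents do not support:
- **The comparison is biased.** It is not: subjects are re-randomised after Week 10 status is known, and simulated type I error is unaffected.
- **Week 10 response is the strongest predictor, so precision is being given away free.** No document quantifies its effect, and the gain ranges from nil upward.
- **The 100 mg test suffers most because it runs at 0.025.** The plan gives no Week 10 endoscopic rate for 100 mg, and alpha can pass to that sequence from the other.

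**Conclusion.** The omission is real and unredacted, and worth correcting, but it is a point of efficiency and chance imbalance rather than validity. At the 200 mg planning rates 37.5% of entrants start without the response being tested, and the arms' shares differ by chance with an SD of about 7.7 points. Adjustment is worth about 0 to 1 power point at 50% v 20%, and about 1 to 6 points at 40% v 20%, for assumed odds ratios of 2 to 6. The upper figures need effective pooling and an immunomodulator effect that is weak. If Week 10 response is not prognostic, there is no gain.

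**What to change.** Before unblinding, amend SAP 6.2.4 for endoscopic response at Week 58 in the Maintenance Study:
- Add endoscopic response at Week 10 (yes/no) to the CMH test and the stratum-adjusted difference, alongside the three existing factors.
- State the minimum stratum size and the order of pooling, for example collapsing over immunomodulator use first. This makes the aggregation that the SAP already allows into a rule.
- Apply the same rule to the Week 58 composite of PRO2 remission and endoscopic response, which takes its method from 6.2.4 through SAP 6.3.2.
- Record the extra factor in SAP 6.6 as a change from the protocol-specified analysis.

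Leave the re-randomisation factors alone.

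The cost is a few lines of SAP text and no new data. SAP 2.2 breaks the blind only after the Maintenance Study is complete, which leaves room for the change. The downsides are more strata before pooling, a slight loss of power if Week 10 response turns out not to be prognostic, and different strata for the two co-primary endpoints.

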### **4.2. Induction Study (Cohorts A and B)**

#### **4.2.1. Inclusion Criteria**

Subjects must meet all of the following inclusion criteria to be eligible for participation in either the Cohort A or B Induction Study.

- 1) Must have the ability to understand and sign a written ICF, which must be obtained prior to initiation of study procedures
- 2) Males or non-pregnant, non-lactating females, ages 18 to 75 years, inclusive based on the date of the screening visit
- 3) Females of childbearing potential (as defined in [Appendix 7](#)) must have a negative serum pregnancy test at screening and a negative urine pregnancy test at baseline
- 4) Male subjects and female subjects of childbearing potential who engage in heterosexual intercourse must agree to use protocol specified method(s) of contraception as described in [Appendix 7](#)

- 5) Documented diagnosis of CD with a minimum disease duration of 3 months with involvement of the ileum and/or colon at a minimum, documented by the following:
  - a) Medical record documentation of, or an ileocolonoscopy (full colonoscopy with the intubation of terminal ileum) report dated  $\geq 3$  months before enrollment, which shows features consistent with CD, determined by the procedure performing physician AND
  - b) Medical record documentation of or a histopathology report showing features consistent with CD, determined by the pathologist.
- 6) Moderately or severely active CD as defined by:
  - a) CDAI total score between 220 and 450 inclusive (refer to [Appendix 4](#)), AND
  - b) PRO2 score consisting of abdominal pain  $\geq 2$  (on CDAI scale of 0 to 3) OR daily stool frequency  $\geq 4$  (refer to [Appendix 4](#)), AND
  - c) Evidence of active disease as measured by SES-CD (refer to [Appendix 5](#)) based on central reading:
    - i) Total score  $\geq 6$ , OR
    - ii) If disease is limited to the ileum and/or right colon, a combined score  $\geq 4$  in these two segments
- 7) Meet one of the following TB screening criteria:
  - a) No evidence of active or latent TB ie,
    - i) A negative QuantiFERON® TB-Gold In-Tube test (or centrally reported equivalent assay) at screening, AND
    - ii) A chest radiograph (views as per local guidelines) taken at screening or within the 3 months prior to screening (with the report or films available for investigator review) without evidence of active or latent TB infection, AND
    - iii) No history of either untreated or inadequately treated latent or active TB infection
  - b) Previously treated for TB: ie, if a subject has previously received an adequate course of therapy as per local standard of care for either latent TB (eg, 9 months of isoniazid in a location where rates of primary multi-drug resistant TB infections are  $< 5\%$  or an acceptable alternative regimen) or active TB (acceptable multi-drug regimen). In these cases, no QuantiFERON® TB-Gold In-Tube test (or centrally reported equivalent assay) need be obtained, but a chest radiograph must be obtained if not done so within 3 months prior to screening (with the report or films available for investigator review). It is the responsibility of the investigator to verify the adequacy of previous anti-TB treatment and provide appropriate documentation.

- c) Newly identified latent TB during screening: ie, a subject who has a newly identified positive diagnostic TB test result (defined as a positive QuantiFERON® TB Gold in Tube test [or centrally reported equivalent assay]) in which active TB has been ruled out and for which appropriate, ongoing, prophylactic treatment for latent TB has been initiated for a minimum of 4 weeks prior to the first administration of study medication. Adequate treatment for latent TB is defined according to local country guidelines for immunocompromised subjects. Quantiferon testing may not be repeated except in the case of a single repeat for indeterminate results.

Cases falling under category “b” and “c” need to be approved by the Sponsor prior to enrollment in the study. No subject with currently ACTIVE TB may be enrolled in the study, regardless of past or present anti-TB medication use.

- 8) Laboratory parameters (subjects who fail to meet below reference laboratory tests may be re-tested once at discretion of investigator prior to being considered a screen failure):
  - a) Hepatic panel (AST, ALT, total bilirubin)  $\leq 2$  times ULN
  - b) Estimated CrCl  $\geq 40$  ml/min as calculated by the CC&G equation
  - c) Hemoglobin  $\geq 8$  g/dL (both males and females)
  - d) Absolute neutrophil count (ANC)  $\geq 1.5 \times 10^9/L$  (1,500/mm^3)
  - e) Platelets  $\geq 100 \times 10^9/L$
  - f) White blood cells (WBC)  $\geq 3.0 \times 10^9/L$
  - g) Absolute lymphocyte count  $>750/mm^3$
- 9) May be receiving the following drugs (subjects on these therapies must be willing to remain on stable doses for the noted times):
  - a) Oral 5-aminosalicylate (5-ASA) compounds provided the dose prescribed has been stable for at least 4 weeks prior to randomization; dose must remain stable for the first 10 weeks after randomization
  - b) Azathioprine or 6-MP or MTX provided the dose prescribed has been stable for 4 weeks prior to randomization; dose must remain stable for the first 10 weeks after randomization
  - c) Oral corticosteroid therapy (prednisone prescribed at a stable dose  $\leq 30$  mg/day or budesonide prescribed at a stable dose of  $\leq 9$  mg/day) provided the dose prescribed has been stable for 2 weeks prior to randomization; dose must remain stable for the first 14 weeks after randomization
  - d) Antibiotics for the treatment of CD (eg, metronidazole, ciprofloxacin) provided the dose prescribed has been stable for 2 weeks prior to randomization. Dose must remain stable for the first 10 weeks after randomization. Subjects who are on cyclic therapy must continue their standard low-dose regimen without change for the first 10 weeks after randomization.

10) Willingness to refrain from live or attenuated vaccines during the study and for 12 weeks after last dose.

11) Must be up to date on colorectal cancer screening and surveillance as standard of care according to local guidelines.

